3.3 Explatory analyses

3.3.1 Bias derived by CI

By the CI measurement from Swan-Ganz, FloTrac, and ClearSight, the variable bias (X) is derived for statistical analysis:

$$x_{ij} = CI_{tij} - CI_{rij} = (CO_{tij} - CO_{rij})/BSA$$

Where x_{ij} is the bias of ith subject and jth matched pair repeated measurements of CI, CI_{tij} is CI measurement of the ith subject at jth repeated measurement by FloTrac and ClearSight, CI_{rij} is the CI measurement of ith subject at jth repeated measurement of reference device, Swan-Ganz ITD, on the same study subject. Here i=1,...,n (the estimated sample size, 102), j=1,...,m (the planned repeated measurements, 8). And BSA is the body surface area of this study subject.

$$PE_{ij} = 100 * \frac{|CO_{tij} - CO_{rij}|}{CO_{rij}} = 100 * \frac{|x_{ij}|}{CO_{rij}}$$

3.3.2 PE derived by CI

The percent error of CI is derived as follow:

$$PE_{ij} = 100 * \frac{|CI - CI_{rij}|}{CI_{rij}} = 100 * \frac{|x_{ij}|}{CI_{rij}} = 100 * \frac{\left|\frac{CO_{tij}}{BSA} - \frac{CO_{rij}}{BSA}\right|}{\frac{CO_{rij}}{BSA}} = 100 * \frac{|CO_{tij} - CO_{rij}|}{CO_{rij}}$$

	Revision Date: De	ecember 2, 2020	Rev	В	For Use Only by Affiliates of Edwards Lifesciences	Page 14
Edwards	Title	Statistical Analysis Pl Nonrandomized, Obso Monitoring in Pediatri	ervatio	onal St		

where PE_{ij} is the percent error of CI measurement of ith subject at jth repeated measurements by FloTrac and ClearSight, using Swan-Ganz ITD CI measurement as the reference. BSA is the body surface area of this study subject. Here the PE calculated by CI is the same as calculated by CO. Therefore, this fact will be noted and present in the final report.

$$x_{ij} = CO_{tij} - CO_{rij}$$

3.4 Explatory analyses

3.4.1 98.75% Confidence Intervals for PE using bootstrap method (derived by CO and CI)

Bootstrap method will be used to estimate one-sided confidence for PE, CO and CI measures under study. This will be performed for all analysis datasets as well as those datasets with rejected data. Results will be compared.

	Revision Date: De	ecember 2, 2020	Rev	В	For Use Only by Affiliates of Edwards Lifesciences	Page 15
Edwards	Title	Statistical Analysis Pl Nonrandomized, Obso Monitoring in Pediatri	ervatio	onal St		

4. ANALYSIS POPULATIONS

The analysis set is composed of all evaluable subjects with valid CO matched paired measurements from the target medical device system (Swan-Ganz[™], FloTrac[™], and ClearSight[™]), the Fick principle and the reference medical device system (a Swan-Ganz thermodilution catheter). Evaluable subjects are those with non-rejected intermittent thermodilutions who have completed the 30-day telephone follow up period.

5. **DEFINITIONS**

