For PE, a sample size of n=60 will be used in the study design, after considering two pairwise comparisons between 2 devices with a reference device. In addition, after considering a 34.5% rejection rate for hemodynamic instability, 10% lost to follow-up rate, 102 evaluable subjects will be targeted. To account for the learning curve and 6 additional Roll-in Subjects will be enrolled, totaling 108 Subjects enrolled in the study.

Calculation of Cardiac Index (CI)

Adjusting cardiac output (CO) with study subject body surface area (BSA) results in the derivation of cardiac index (CI). This adjustment for body surface area, in the study pediatric population (12 to 18 years old), will result in a smaller bias and percent error between test device and reference device. The standard deviation estimate will also be smaller, at the same scale, thus, the sample size estimate decreases. Sample size estimates for bias and percent error for CI is detailed in the SAP.

THIS DOCUMENT CONTAINS CONFIDENTIAL AND PROPRIETARY INFORMATION OF EDWARDS LIFESCIENCES, LLC. IT MAY NOT BE REPRODUCED OR DISCLOSED WITHOUT PRIOR WRITTEN PERMISSION FROM EDWARDS LIFESCIENCES, LLC.

POGO Study		
Study #2019-08		

Primary Safety Endpoint

The primary safety endpoint is to assess all serious intraoperative and post-operative adverse events through 30 days, including serious device-related events.

Analysis Populations

All enrolled subjects with evaluable data will be included in the analysis of effectiveness endpoint, and all enrolled subjects will be included in the analysis of safety endpoint.

The analysis set is composed of all evaluable subjects with valid CO matched pair measurements from the target medical device system (FloTrac and ClearSight systems) and the reference medical device system (the Swan-Ganz thermodilution pulmonary artery catheter).

Evaluable subjects are those with non-rejected intermittent thermodilutions who have completed the 30-day telephone follow up period.

Analysis Methods

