8. SCHEDULE OF EVENTS & PROCEDURES

Schedule of Events

Lifesciences Corporation.

The following matrix shows the scheduled assessments through the end of the Study (30-Day Follow Up).

Study Procedure / Exam	Subject Screening	Procedure	Discharge	30-Day Follow Up (±14 Days)
Obtain Informed Consent	X	7 10000.010	2.00.10.180	(==: ==;
Perform Inclusion / Exclusion Evaluation	Х			
Obtain Medical History / Subject Demographics ¹	Х			
Assign Subject ID		Х		
Enter Subject Data into Monitor		Х		
Vital Signs		Х		
Monitoring Duration		Х		
Data download from Monitor		Х		
Obtain Fluid and Vasoactive Medication Administration Record ²		Х		
Complete eCRFs	Х	Х	Х	Х
Record Adverse Events, if applicable		Х	Х	Х
Phone Contact 30-day follow up / Mortality Determination				х

The duration of individual study participation is expected to be 30 days (±14 days) after procedure.

Data collection will occur during the study via the HemoSphere platform and electronic case report forms (eCRFs). The 30-day follow-up phone contact will be recorded on the applicable eCRF.

2019-08 Page **26** of **52 CONFIDENTIAL**

¹ Medical History / Subject Demographics / Surgical and Clinician Demographics can be obtained prior to procedure, either at the screening visit or on the day of procedure.

² Can be collected via the hospital record system anytime on the day of procedure or thereafter.

THIS DOCUMENT CONTAINS CONFIDENTIAL AND PROPRIETARY INFORMATION OF EDWARDS LIFESCIENCES, LLC. IT MAY NOT BE REPRODUCED OR DISCLOSED WITHOUT PRIOR WRITTEN PERMISSION FROM EDWARDS LIFESCIENCES, LLC.

Edwards Lifesciences, Edwards, the stylized E logo, HemoSphere, Swan-Ganz, FloTrac, ClearSight and ForeSight Elite are trademarks of Edwards

P(OGO Study	ĺ
St	tudy #2019-08	ì

Intermittent Thermal Dilution Assessment(s)

Using the Swan-Ganz thermodilution pulmonary artery catheter, two series of four (4) intermittent dilutions should be administered by the Investigator while in the cath lab. The dilution curves are analyzed and averaged to give one (1) CO value.

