CO measured by the ClearSight and FloTrac systems will be simultaneously compared with the CO measured by the Swan-Ganz catheter using the thermodilution method. There will be 2 sets of 4 measurements recorded over a 30-second interval, during the Swan-Ganz thermodilution bolus injection. Those 4 measurements will be pair-matched by time in the ClearSight and FloTrac systems. The same number of measurements that will be recorded during the Swan-Ganz thermodilution will be recorded for the ClearSight and FloTrac devices. The following thermodilution procedure will be used:

A 10 ml sample of iced glucose solution (5%) will be drawn through an iced injectate container (CO-SET+ or any other container that meets the requirements, as determined by the investigator) and injected in a steady manner. Four TD CO determinations will output, preferably within 5 minutes. From there, three values, will be averaged to obtain one single value. Each thermodilution curve will be visually checked before acceptance. The dilution curve will be automatically corrected for the temperature of the blood and of the injectate measured at the entrance of the catheter lumen. Values for temperatures will be stored together with the thermodilution values. The entire series of four thermodilution estimates will be rejected if, during an injection, the HemoSphere advanced monitor displays an alert signal, if the injectate temperature is above 10 °C, or when the curve of the dilution is abnormal. In case of rejection, the entire series of four thermodilutions will be repeated.

Hemodynamics and respiratory rate must be stable during the TD series, since variability violates the assumption of stability that is required for the TD technique. Sponsor-instream review of the TD series will occur after each catheterization to determine if hemodynamic variability occurred and the site team will be retrained on the importance of conducting the TD technique during hemodynamic stability.

Clinical Study Completion or Early Termination

The IRB will be notified upon completion or premature termination of the study. Edwards retains the right to suspend or prematurely terminate this clinical study at any time.

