13. DATA COLLECTION METHODS

Study data will be captured utilizing electronic Case Report Forms (eCRFs) including the 30-day follow-up call as well as downloaded files captured directly via the use of the HemoSphere advanced monitor. Data collected from the HemoSphere advanced monitor will be downloaded at the end of each catheterization procedure and stored on a USB stick. USBs will be stored in a secure location at the site, accessible only to Study site personnel. The HemoSphere data on USBs may be shipped to the Sponsor at any point in time of the study per the request of the Sponsor.

POGO Study	
Study #2019-08	

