2.2 Overall Study Design and Plan

This is an observational study in the U.S. A subject will be considered enrolled in the study once the subject has signed the informed consent, a Swan-Ganz catheter has been deployed, a FloTrac has been connected, a ClearSight finger cuff has been attached and ForeSight Elite sensors have been placed. The Study ID will be a 6-digit number, the first three numbers will identify the site, and the second set of numbers will identify the subject identification number. Subjects will be enrolled in age group, 12 to 18 years of age.

A Swan-Ganz catheter, FloTrac transducer, ClearSight finger cuff and ForeSight Elite sensors will be placed prior to the start of the surgery. There will be 2 sets of 4 intermittent cardiac output measurements recorded, each over a 30 second interval during the bolus injection. Measures for FloTrac and ClearSight will be retrospectively matched by time point to the Swan-Ganz catherization data. Intermittent cardiac output and other hemodynamic parameters will be collected throughout the duration of the surgery. For each study subject two sets of four repeated measurements will be taken in the cardiac catherization lab. Data collected in this study will support in expanding the current indications of Swan-Ganz, FloTrac and ClearSight into the pediatric population.

In order to avoid a learning curve bias, up to 6 roll-in subjects will be enrolled, which is counted in the final sample size in study. The collected data from the roll-in cohort will be analyzed separately from the pivotal study subjects.

A modified intent-to-treat (mITT) principle will be applied. Through investigator professional judgement and statistical principles, this study will be conducted in a manner that is consistent with the applicable regulations and in accordance with current Good Clinical Practice (GCP).

All methods of measurements will be recorded for all devices and included as part of the data set. Edwards will conduct analyses both with and without observations that are determined to be outliers. Once outliers are identified, the Principal Investigator will assess the validity of the data.

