3. STUDY ENDPOINTS

The primary effectiveness endpoint is to demonstrate that monitoring of cardiac output (CO) with Swan-Ganz, FloTrac, and ClearSight is comparable as determined by the Bland-Altman method of bias.

The secondary endpoint analyses will include:

CO, assessed using include using the Critchley and Critchley method of percent error calculation

Two comparisons will be performed for each of three endpoints described above: FloTrac vs Swan-Ganz and ClearSight vs Swan-Ganz.

The primary and secondary efficacy endpoints will be analyzed using the evaluable analysis set as defined in Section 5.

The primary safety endpoint is to assess all serious intraoperative and post-operative adverse events through 30 days, including serious device-related events. The safety endpoint will be analyzed using the safety analysis set as defined in Section 5.

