5.2. Evaluable Subject

An evaluable subject is one who has valid CO pair measurements that were not rejected and also has completed the 30-Day follow up.

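### Completing the 30-day safety call is a condition for entering the cardiac output analyses, so up to about 7 of 67 subjects with valid data would be dropped

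*Combined protocol and SAP*

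**What the plan says.** **Who is evaluable.** Protocol section 6 (Analysis Populations) and SAP section 4 share one sentence: "Evaluable subjects are those with non-rejected intermittent thermodilutions who have completed the 30-day telephone follow up period". SAP section 5.2 repeats the condition: "An evaluable subject is one who has valid CO pair measurements that were not rejected and also has completed the 30-Day follow up".

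**Where the set is used.** SAP section 3: "The primary and secondary efficacy endpoints will be analyzed using the evaluable analysis set as defined in Section 5".

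**When CO is measured.** Protocol section 8: "There will be 2 sets of 4 measurements recorded over a 30-second interval, during the Swan-Ganz thermodilution bolus injection". SAP section 2.2: "For each study subject two sets of four repeated measurements will be taken in the cardiac catherization lab". Protocol section 13: "Data collected from the HemoSphere advanced monitor will be downloaded at the end of each catheterization procedure".

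**What the 30-day contact collects.** The schedule in protocol section 8 lists adverse events, case report forms and "Phone Contact 30-day follow up / Mortality Determination". The schedule in SAP section 7.5 lists adverse events and the call. Neither has a CO measurement at that visit.

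**The safety analysis.** Protocol section 6 does not attach the call to it: "all enrolled subjects will be included in the analysis of safety endpoint".

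**Sample size.** SAP sections 2.3.1 and 2.3.2 start from 60 analysed subjects, allow 34.5% for rejection and 10% for loss to follow-up, and reach 102 pivotal subjects plus 6 roll-ins, 108 in all.

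**The concern.** The effectiveness question is whether two devices agree with thermodilution at one moment in the catheterization laboratory. Those data are complete when the monitor is downloaded. A telephone call about a month later cannot make a CO pair more or less valid, and the documents give no reason for requiring it. The condition is placed on the analysis that does not use the call and left off the one that does.

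Two things are at stake. Valid primary and secondary data are thrown away. And membership of the analysis set comes to depend on something that happens after the measurement: read literally, a subject who dies, withdraws or cannot be reached before the call leaves the device comparison despite having valid pairs. Protocol section 9 lists 30-day mortality among the anticipated risks. Protocol section 12 lets the investigator keep using information gathered before an authorization is revoked, so later loss of contact does not in itself make the pairs unusable.

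**Working it through.** **Inputs.** Analysed n of 60, 34.5% rejection, 10% loss to follow-up and 102 pivotal subjects (SAP 2.3.1 and 2.3.2). Alpha 0.025 per comparison (same sections). Bias: margin 0.5 L/min, true bias 0, SD 0.991 after the ICC adjustment (SAP 2.3.1). Percent error: SD 70%, or 69.38% after the ICC adjustment (SAP 2.3.2).

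**1. The plan's own figure reproduces.**
- 60 / [(1 − 0.345) × (1 − 0.10)] = 60 / 0.5895 = 101.8, rounded up to 102. Adding 6 gives 108.
- The 102 is therefore the number before rejection and loss, although the SAP calls these subjects evaluable.
- The starting 60 is the percent-error sample size. A one-sided, one-sample t-test for a difference of 30 with SD 70 needs 49 at alpha 0.05 and 60 at 0.025. The equivalence test for bias needs 54 at 0.025.

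**2. Subjects dropped only because of the call.**
- With valid pairs: 102 × 0.655 = 66.8, about 67.
- Also completing the call: 66.8 × 0.90 = 60.1, about 60.
- Dropped: 66.8 − 60.1 = 6.7, about 7.

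This takes 34.5% as a per-subject rate and assumes that the whole 10% falls on subjects who already have valid pairs, independently of rejection. If half of the 10% is lost earlier (my assumption), 102 × 0.655 × 0.95 = 63.5 have valid pairs and about 3 are dropped. If all of it is lost earlier, none is dropped. The 10% is a planning allowance; actual call loss could be higher or lower.

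**3. Cost in precision.** Interval width varies as 1/√n: √(67/60) = 1.057, so about 6% wider at 60 than at 67.

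**4. Cost in power, at alpha 0.025.**

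| Endpoint | n = 60 | n = 67 |
|---|---|---|
| Bias (SD 0.991, true bias 0) | 94.0% | 96.5% |
| Percent error (difference 30, SD 69.38%) | 90.9% | 93.7% |

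The percent-error row needs a caveat. SAP 2.3.2 describes the 30% as the assumed true mean, which equals the acceptance limit; read literally, power would be 2.5% at any n. Treating it as a difference of 30 is what reproduces the plan's 49 and 60, but against a 30% limit it implies a true percent error of zero. I use it only to stay on the plan's own scale.

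**5. Margin at n = 60.** For percent error with SD 69.38%, power is 90.9% at 60, 90.4% at 59 and 89.9% at 58: a margin of about one subject. With the unadjusted 70% it is 90.4% at 60 and 89.9% at 59.

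**6. Greater call loss.** At 20% (an assumption that nothing in the documents supports), 102 × 0.655 × 0.80 = 53.4. At n = 53, power is 87.1% for percent error (SD 69.38%) and 90.0% for bias.

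**The case against.** **The loss is budgeted.** This is the strongest objection, and it stands as far as it goes. A reader might infer that the rule leaves the study underpowered. The plan does not support that: the 10% is built into the 102, and at that loss both endpoints keep at least 90% power. Only a higher, assumed call loss takes percent error below target, and bias still has 90.0% at the 20% illustrated. The follow-up window of ±14 days also gives sites some room to make contact.

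**Bias has not been shown.** A reader might infer that the retained subjects give a distorted answer. The documents offer no mechanism linking a missed call to device disagreement, and no direction can be assigned. What stands is that selection after measurement is avoidable and serves no stated purpose.

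**Percent error has some room.** A reader might infer that 60 leaves no slack at all. That holds only with the unadjusted SD of 70%; with the plan's ICC-adjusted 69.38%, 59 subjects still meet the target.

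**Other text may bring these subjects back.** SAP 2.2 says a modified intent-to-treat principle applies, and SAP 5.3 places exposed subjects in the effectiveness dataset. Protocol section 6 also opens by admitting enrolled subjects who have evaluable data. SAP 3.1.2 and 3.4.1 run bootstrap intervals on every analysis dataset. It would therefore go too far to say that no planned analysis could restore subjects without a call. But SAP section 3 assigns the primary and secondary endpoints to the evaluable set. No passage clearly commits to reporting those tests on the modified intent-to-treat set. The stated comparisons restore rejected values (SAP 3.1.2, 3.4.1, 6.3), and the subject-level sensitivity analysis removes subjects (SAP 8.3.1). The conflict needs settling; it does not cancel the condition.

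**Conclusion.** The point holds, at modest size. As written, the effectiveness set leaves out subjects with complete, valid CO pairs because of a later safety contact. On the plan's figures this is up to about 7 of 67, with a range of 0 to 7 depending on how much of the 10% is lost before valid pairs exist, and more if calls are missed more often than planned. The consequence at the planned loss is an interval about 6% wider and roughly 2.5 to 3 points of power forgone (96.5 − 94.0 = 2.5 for bias; 93.7 − 90.9 = 2.8 for percent error), together with an unnecessary selection step of unknown direction. It is not a loss of planned power, and the documents do not show that any conclusion would change. The figures assume that all 102 pivotal subjects are enrolled and that the SAP's rates apply per subject; the percent-error powers also rest on the difference-of-30 reading. The change is worth making because it costs almost nothing and should be settled before the data are analysed.

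**What to change.** 1. Delete the 30-day completion condition from the effectiveness set in protocol section 6, SAP section 4 and SAP section 5.2. Define that set as pivotal subjects with valid, non-rejected matched CO pairs under the existing rejection and averaging rules. Keep the 30-day follow-up for safety only.
2. Keep enrolment at up to 108. State in the sample-size text that about 60 to 67 subjects are expected in the effectiveness analyses. Say openly that the 10% then becomes a reserve for loss before valid pairs are obtained, for which the documents give no separate rate, and that with no such loss 60 / 0.655 = 91.6, so 92 pivotal subjects (98 with roll-ins), would suffice.
3. Reconcile the modified intent-to-treat wording in SAP 2.2 and 5.3, and the reference to all analysis datasets in SAP 3.1.2 and 3.4.1, with SAP section 3 by naming the set used for the primary and secondary effectiveness tests.

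The cost is wording in three definitions, a short addition to the sample-size text and one clarification of the analysis sets. Data collection, rejection criteria, averaging and maximum enrolment do not change.

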5.1. Enrolled Subject

A subject will be considered enrolled in the study once the subject has signed the informed consent, a Swan-Ganz catheter has been deployed, a FloTrac has been connected, a ClearSight finger cuff has been attached and/or ForeSight Elite sensors have been placed.

5.2. Evaluable Subject

An evaluable subject is one who has valid CO pair measurements that were not rejected and also has completed the 30-Day follow up.

5.3. Modified Intent-to-treat (mITT)

Modified Intent-to-treat (mITT) is defined as the study subjects who were exposed to the study product and will therefore be included in the effectiveness and safety analysis datasets.

5.4. Per Protocol Analysis

A per protocol analysis is defined as a dataset of subjects who completed the cardiac catherization as written in the protocol. No protocol deviations occurred during the cardiac catherization procedure.

5.5. Pivotal Cohort

The pivotal cohort are subjects who were enrolled after the roll-in period. The pivotal cohort will be analyzed separately from the roll-in cohort.

	Revision Date: De	ecember 2, 2020	Rev	В	For Use Only by Affiliates of Edwards Lifesciences	Page 16
Edwards	Title	Statistical Analysis P Nonrandomized, Obso Monitoring in Pediatri	ervatio	onal St		•

5.6. Roll-in Cohort

The roll-in cohort are the first 1-3 subjects enrolled at the site that the study investigator uses to confidently perform the intermittent thermodilution. This group of patients will analyze separately from the pivotal subjects.

